2.7.4 Deaths and Serious Adverse Events

In the event that a subject has withdrawn consent, no data after the withdrawal of consent date from this subject including death is supposed to appear in the database, which should be part of the data cleaning process.

Separate summaries for on-treatment and all deaths (on-treatment and post-treatment) will be produced. All deaths will be summarized by treatment arm and primary cause of death. All deaths will be listed, post treatment deaths will be flagged.

All SAEs will be tabulated based on the number and percentage of subjects who experienced the event. Separate summaries will also be provided for study treatment-related SAEs. The summary tables will be displayed in descending order of Octreotide+Lap+Cap group by SOC and PT.

A study treatment-related SAE is defined as an SAE for which the investigator classifies the relationship to study treatment as “Yes”. A worst case scenario approach will be taken to handle missing data, i.e. the summary table will include events with the relationship to study treatment as ‘Yes’ or missing.

SAEs are included in the listing of all adverse events with flag for fatal AEs.

2.7.5 Adverse Events Leading to Discontinuation of Study Treatment and/or Withdrawal from the Study

The following categories of AEs will be summarized separately in descending order of Octreotide+Lap+Cap group by SOC and PT and separate supportive listings will be generated with subject level details for those subjects:

- AEs leading to discontinuation of octreotide
- AEs leading to discontinuation of lapatinib
- AEs leading to discontinuation of capecitabine
- AEs leading to withdrawal from the study

2.7.6 Clinical Trial Safety Disclosure

For the legal requirements of ClinicalTrials.gov and EudraCT, two required tables on treatment emergent adverse events which are not serious adverse events with an incidence greater than 5% and on treatment emergent serious adverse events and SAE suspected to be related to study treatment will be provided by system organ class and preferred term on the safety set population.

If for a same patient, several consecutive AEs (irrespective of study treatment causality, seriousness and severity) occurred with the same SOC and PT:

a single occurrence will be counted if there is ≤ 1 day gap between the end date of the preceding AE and the start date of the consecutive AE

more than one occurrence will be counted if there is > 1 day gap between the end date of the preceding AE and the start date of the consecutive AE

For occurrence, the presence of at least one SAE / SAE suspected to be related to study treatment / non SAE has to be checked in a block e.g., among AE's in a ≤ 1 day gap block, if at least one SAE is occurring, then one occurrence is calculated for that SAE.

The number of deaths resulting from SAEs suspected to be related to study treatment and SAEs irrespective of study treatment relationship will be provided by SOC and PT.

2.7.7 Pregnancies

While pregnancy itself is not considered to be an AE or SAE, any pregnancy complication or elective termination of a pregnancy for medical reasons will be recorded as an AE or SAE as described in the protocol. If subjects become pregnant while on the study, the information will be included in the narratives and no separate table or listing will be produced.

2.7.8 Clinical Laboratory Evaluations

The assessment of laboratory toxicities will examine the following laboratory tests:

Hematology:

- Hemoglobin (HGB),
- Hematocrit (HCT),
- Red Blood Cell (RBC) count,
- White Blood Cell (WBC) count,
- Total Neutrophils,
- Lymphocyte count
- Monocytes
- Eosinophils
- Basophils
- Platelet count.

Hematocrit, monocytes, eosinophils, basophils and RBC are not gradable by NCI-CTCAE v4.03.

Clinical Chemistry:

- Sodium,
- Potassium,
- Ionised Calcium,
- Glucose,
- Urea/Blood Urea Nitrogen (BUN)
- Creatinine,
- Estimated Creatinine Clearance,
- Albumin,
- Total Protein

Estimated Creatinine Clearance and Total Protein are not gradable by CTCAE v4.03. For Sodium, Potassium, Ionised Calcium and Glucose there will be two bi-directional parameters (hyper and hypo) created, and the tests will be graded by NCI-CTCAE v4.03 in both directions.

Liver Function Tests (LFT):

- Aspartateaminotransferase (AST)
- Alanine aminotransferase (ALT)
- Alkaline phosphatase
- Total bilirubin (total)

- Direct bilirubin.

All these tests are gradable by NCI-CTCAE v4.03.

Coagulation Tests:

- Prothrombin time (PT)
- International Normalized Ratio (INR)
- Activated partial thromboplastin time (APTT).

INR and APTT are gradable by NCI-CTCAE v4.03 and PT is not.

Urinalysis:

Dipstick urinalysis; if dipstick urinalysis showed $\geq 2+$ urine protein, then a 24-hour urine protein must be assessed. It is not gradable by NCI-CTCAE v4.03.

Laboratory grades will be reported using NCI-CTCAE v4.03.

Summaries of lab data by maximum toxicity grade will be provided.

Summaries of worst case grade increase from baseline grade will be provided for all the lab tests that are gradable by NCI-CTCAE v4.03. These summaries will display the number and percentage of subjects with a maximum post-baseline grade increasing from their baseline grade. Any increase in grade from baseline will be summarized along with any increase to a maximum grade of 3 and any increase to a maximum grade of 4. Missing baseline grade will be assumed as grade 0. For laboratory tests that are graded for both low and high values, summaries will be done separately and labeled by direction, e.g., sodium will be summarized as hyponatremia and hypernatremia.

For lab tests that are not gradable by NCI-CTCAE v4.03, summaries of worst case changes from baseline with respect to normal range will be generated. Decreases to low, changes to normal or no changes from baseline, and increases to high will be summarized for the worst case post-baseline. If a subject has a decrease to low and an increase to high during the same time interval, then the subject is counted in both the “Decrease to Low” categories and the “Increase to High” categories. In addition, the summary will include worst case changes from baseline with respect to normal range by scheduled visits.

Separate summary tables for hematology, chemistry and liver function laboratory tests will be produced.

A supporting listing of laboratory data for subjects with abnormalities of potential clinical concern will be provided. A separate listing of laboratory data with character values will also be provided.

Detailed derivation of baseline assessment is specified in [Section 2.1.3.6](#).

Unless otherwise specified, the denominator in percentage calculation will be based on the number of subjects with non-missing value at each particular visit.

2.7.8.1 Analyses of Liver Function Tests

Summaries of hepatobiliary laboratory events including possible Hy's law cases will be provided.

Possible Hy's law cases are defined as any elevated $ALT > 3 \times ULN$, total bilirubin $\geq 2 \times ULN$ and $ALP < 3 \times ULN$ /missing. Total bilirubin $\geq 2 \times ULN$ can be within 28 days following the ALT elevation and if direct bilirubin is available on the same day, it must be $\geq 35\%$ of total bilirubin. $ALP < 3 \times ULN$ /missing means the criteria is satisfied unless the ALP is $\geq 3 \times ULN$ at any time of bilirubin elevation within the 28 days window.

2.7.8.2 Lab values of Potential Clinical Importance

Reference ranges for all laboratory parameters collected throughout the study are provided by the laboratory. A laboratory value that is outside the reference range is considered either high abnormal (value above the upper limit of the reference range) or low abnormal (value below the lower limit of the reference range). Note: a high abnormal or low abnormal laboratory value is not necessarily of clinical concern. The laboratory reference ranges will be provided on the listings of laboratory data. Clinical laboratory test results outside of the reference range will be flagged in the listings.

To identify laboratory values of potential clinical importance, NCI-CTCAE v4.03 will be used to assign grades to the relevant laboratory parameters.

For laboratory data which are not listed in the NCI-CTCAE v4.03, a summary of values outside the normal range will be provided.

2.7.9 Other Safety Measures

Unless otherwise specified, the denominator in percentage calculation will be based on the number of subjects in safety set.

Vital Signs

In addition vital signs values will be categorized as follows:

- Systolic BP (mmHg): Grade 0 (< 120), Grade 1 (≥ 120 - < 140), Grade 2 (≥ 140 - < 160) and Grade 3 (≥ 160)
- Diastolic BP (mmHg): Grade 0 (< 80), Grade 1 (≥ 80 - < 90), Grade 2 (≥ 90 - < 100), and Grade 3 (≥ 100)
- Heart rate (beats/min): < 60 , 60-100, and > 100

Summaries of increase in vital signs from the baseline with respect to the categories defined above will be performed. These summaries will display the number and percentage of subjects with any grade increase, increase to grade 2 and increase to grade 3 at the worst case post-baseline.

The following criteria will be used to flag vital sign values that are values of potential clinical importance:

To identify heart rate values of potential clinical importance, NCI-CTCAE v4.03 will be used to assign categories that align with the grades for ‘Sinus bradycardia’, ‘Sinus tachycardia’, ‘Supraventricular tachycardia’, and ‘Ventricular tachycardia’.

Vital Sign Parameter	Potential Clinical Importance (PCI) Range	Unit
Decrease from baseline Heart Rate	Decrease to <60	bpm
Increase from baseline Heart Rate	Increase to >100	bpm

To identify blood pressure values of potential clinical importance, NCI-CTCAE v4.03 will be used to assign categories that align with the grades for ‘Hypertension’.

Vital Sign Parameter	Potential Clinical Importance (PCI) Range	Unit
Increase from baseline Systolic Blood Pressure	≥120 to <140 (Grade 1) ≥140 to <160 (Grade 2) ≥160 (Grade 3)	mmHg
Increase from baseline Diastolic Blood Pressure	≥80 to <90 (Grade 1) ≥90 to <100 (Grade 2) ≥100 (Grade 3)	mmHg

ECG

A summary of the number and percentage of subjects who had normal and abnormal (clinically significant and not clinically significant) ECG findings will be displayed overall at baseline and at 24 week end.

Listings of abnormal ECG findings will be provided.

LVEF

Absolute and relative change from baseline in LVEF will be summarized at 24 week end. Only the post-baseline assessments that used the same method (ECHO or MUGA) as the baseline assessments will be used to derive the change from baseline.

LVEF results will also be listed with subject level details including absolute/relative change from baseline and abnormal ECHO / MUGA findings.

To identify LVEF values of potential clinical importance, NCI-CTCAE v4.03 will be used to assign categories that align with the grades for ‘Ejection fraction decreased’.

LVEF Parameter	Potential Clinical Importance (PCI) Range	Unit
Relative change from baseline LVEF	≥20 decrease and below LLN	%

Liver Events

For any liver events that occur during the study, the liver event information will be summarized, including

- whether the subject was age 55 or over,
- whether the subject became pregnant,
- whether a liver imaging was normal or not,
- whether a biopsy was taken or not,
- whether there was fasting or significant dietary change,
- whether the subject took any unconventional medications, if yes, timing when the unconventional medications taken (on treatment or after stopping treatment)
- summary statistics for time from first dose to start of liver event
- summary statistics for time from last dose to start of liver event.

If the number of events does not support a summary, then only listings will be produced.

For subjects with multiple events, the first event will be used for the summary tables. All events with subject level details will be displayed in a supporting listing.

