#### 1.3.1. Risk Assessment

The analysis of risk associated with octreotide treatment in LAP117314 is based primarily on potential risks identified in the [Octreotide SPC](#). These risks are considered relative to the subject population and study treatments and procedures in LAP117314.

Octreotide LAR is approved for use in patients in whom initial treatment with octreotide in the formulation for s.c. injection has been shown to be effective and well tolerated. Prior treatment with octreotide is not required for subjects to be enrolled in LAP117314, and the tolerance to treatment with octreotide is unlikely to be known for most subjects

prior to enrollment in the study. Subjects randomised to receive octreotide must receive one 0.1mg dose of octreotide by s.c. injection to assess tolerability at least one hour before the first dose of the LAR formulation is administered. Following s.c. administration of octreotide, peak circulating concentrations are achieved within 30 minutes, and the elimination half life of octreotide is approximately 100 minutes [Octreotide SPC]. This single s.c. dose of octreotide should identify subjects who have a hypersensitivity reaction to octreotide or its' excipients (the only contraindication for the use of octreotide).

Treatment with octreotide in both the s.c. and LAR formulations is generally well tolerated [McKeage, 2003]. Adverse events related to the mechanism of action of octreotide have been reported, including hyperglycaemia, hypoglycaemia, impaired glucose tolerance, hypothyroidism, thyroid dysfunction and cholelithiasis. These mechanism-related AEs tend to be associated with chronic treatment with octreotide [Octreotide SPC], and are therefore unlikely to be relevant within the context of LAP117314. In this study, octreotide will be administered as only one dose of the s.c. formulation and two doses of the LAR formulation over a period of 28 days, and the total duration of exposure to clinically relevant concentrations of octreotide is expected to be no more than 12 weeks.

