**Table 9 National Cancer Institute common terminology criteria for grading constipation adverse events**

Adverse Event Grade	Constipation
1	Occasional or intermittent symptoms; occasional use of stool softeners, laxatives, dietary modification, or enema
2	Persistent symptoms with regular use of laxatives or enemas; limiting instrumental ADL
3	Obstipation with manual evacuation indicated; limiting self care ADL
4	Life-threatening consequences; urgent intervention indicated
5	Death

ADL=Activities of daily living

Dose reductions and dose delays are permitted during treatment with lapatinib and capecitabine. The procedures to be followed are described in Section 5.10 for lapatinib and in Section 5.11 for capecitabine.

Study completion will be the end of 24 weeks treatment with lapatinib and capecitabine, or disease progression, unacceptable toxicity or subject withdrawal if this is sooner. Serious AEs and other safety data will be reported beyond 24 weeks in subjects who continue treatment with lapatinib and capecitabine until disease progression in countries where the Sponsor is supplying lapatinib and capecitabine. Serious AEs will be followed up until resolution or stabilization of the event or until the subject is lost to follow-up.

The efficacy of prophylactic octreotide in reducing the frequency and severity of diarrhoea is the primary endpoint of this study. Each episode of diarrhoea will be recorded by the investigator as an AE in the eCRF in accordance with the standard AE reporting procedure. Actions associated with the management of diarrhoea (use of anti-diarrhoeal medication, unscheduled visits to healthcare professionals, treatment interruption, rehydration) will be recorded in the eCRF.

Subjects will complete the DMD every week and the FACIT-D every 3 weeks during treatment with lapatinib and capecitabine to provide an additional perspective on the effects of treatment-associated diarrhoea.

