## 4.2. Other Eligibility Criteria Considerations

It is the responsibility of the investigator to ensure all subjects enrolled in LAP117314 are eligible to receive treatment with lapatinib and capecitabine, and meet other criteria described in the Lapatinib, Capecitabine and Octreotide SPCs. In addition to the inclusion criteria (Section 4.1.2) and exclusion criteria (Section 4.1.3), the contraindications, special warnings and precautions for use, and other information included in the Lapatinib, Capecitabine and Octreotide SPCs should be taken into consideration.

Lapatinib, capecitabine and octreotide are contraindicated in subjects with a history of allergic reactions to these drugs, compounds with a similar chemical composition, or excipients associated with these drug formulations. Capecitabine is contraindicated in

subjects with severe leucopenia, neutropenia or thrombocytopenia, or dihydropyrimidine dehydrogenase deficiency.

Caution should be taken in subjects with moderate or severe hepatic impairment. Investigators should consider the subjects hepatic function measures relative to the guidance provided for the management of hepatobiliary AEs in Section 5.13. It is recommended that hepatic function measures prior to randomisation should meet the following criteria:

- Albumin  $\geq 2.5$  g/dL
- Serum bilirubin  $\leq 1.5$  x the upper limit of the normal range (ULN) or  $\leq 2.5$  x ULN with Gilbert's Syndrome
- AST and ALT  $\leq 3 \times$  ULN

Caution should be taken in subjects with severe renal impairment.

Caution should be taken in subjects with conditions that could impair cardiac function, including conditions that could result in prolongation of QTc, arrhythmias and angina pectoris. Subjects with hypertension who are randomised to receive octreotide must be monitored to manage the potential risk of bradycardia associated with octreotide use.

Information on potential interactions with other medicinal products is presented in the Lapatinib, Capecitabine and Octreotide SPCs and in Section 6.2.

Correction of electrolytes (most importantly, potassium, magnesium and calcium) to within normal ranges should take place prior to study entry and during study conduct as clinically indicated.

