**Table 16 Time and events schedule; Subjects who receive octreotide**

	Screen 	Octreotide Dose 1 (Week -1)	Lapatinib and Capecitabine Cycle 			Withdrawal from Study Treatment or End of Study 
			Cycle 1	Cycle 2  (Octreotide Dose 2)	Cycles 3 to 8 	
Procedures						
Informed Consent	x					
Inclusion/Exclusion Criteria	x 	x 				
Demographics	x					
Breast Cancer Medical/Surgical and Treatment History	x					
Efficacy and Safety Assessments						
AE/Toxicity Assessment		x	x	x	x	x 
Disease Assessment	x 	(x) 	(x) 	(x) 	(x) 	x
PROs 		x 	x 	x	x	x
Concurrent Medications	x	x	x	x	x	x
Physical Exam	x					x
Dermatological Exam	x	(x) 	(x) 	(x) 	(x) 	x
Weight, Height, Vital Signs (Temp, BP, pulse)	x					x
ECOG Performance Status	x 					x
Cardiac function	x					x 
ECG	x					(x) 
Lab Assessments						

	Screen 	Octreotide Dose 1 (Week -1)	Lapatinib and Capecitabine Cycle 			Withdrawal from Study Treatment or End of Study 
			Cycle 1	Cycle 2  (Octreotide Dose 2)	Cycles 3 to 8 	
Procedures						
Liver function	x	(x) 	(x) 	(x) 	(x) 	x
Pregnancy Test	x					x
Study Treatments						
Administer Octreotide		x 		x 		
Dispense Lapatinib and Capecitabine			x	x	x	
Assess Lapatinib and Capecitabine Returned				x	x	x

- Schedules for screening assessments are presented in Section 7.1.1 and Section 7.1.2. All screening and baseline assessments must be completed prior to administration of the octreotide 0.1mg s.c. tolerability assessment dose.
- Inclusion and exclusion criteria are presented in Section 4.1.2 and Section 4.1.3, and other considerations are presented in Section 4.2. Investigators must ensure all subjects are eligible to receive treatment with lapatinib and capecitabine in accordance with the Lapatinib SPC and Capecitabine SPC, including evaluation of cardiac function.
- Disease assessment criteria are described in Section 7.1.11.
- ECOG status may be assessed more than once prior to randomisation, but only the assessment within 3 days prior to randomisation will be recorded in the eCRF.

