Administer Octreotide		x ⁸		x ¹³		
Dispense Lapatinib and Capecitabine			x	x	x	
Assess Lapatinib and Capecitabine Returned				x	x	x

1. Schedules for screening assessments are presented in Section [7.1.1] and Section [7.1.2] of the Study Protocol. All screening and baseline assessments must be completed prior to administration of the octreotide 0.1mg s.c. tolerability assessment dose.
 2. Inclusion and exclusion criteria are presented in Section [4.1.2] and Section [4.1.3] of the Study Protocol, and other considerations are presented in Section [4.2] of the Study Protocol. Investigators must ensure all subjects are eligible to receive treatment with lapatinib and capecitabine in accordance with the Lapatinib SPC and Capecitabine SPC, including evaluation of cardiac function.
 3. Disease assessment criteria are described in Section [7.1.11] of the Study Protocol.
 4. ECOG status may be assessed more than once prior to randomisation, but only the assessment within 3 days prior to randomisation will be recorded in the eCRF.
 5. Not mandatory at these visits, but should be conducted in accordance with local clinical practice, at the time of a scheduled 3 weekly visits when possible.
 6. PROs are the FACIT-D and the diarrhoea diary.
 7. To be completed before the octreotide 0.1mg s.c. tolerability assessment dose.
 8. First dose of octreotide LAR to be given 7 days before start of Cycle 1 treatment with lapatinib and capecitabine. Subjects must receive octreotide 0.1mg s.c. at least one hour before the first dose of octreotide LAR to assess tolerability.
 9. **Cycle 2 and Cycle 4 visits are mandatory.** Cycle 3, 5, 6, 7 and 8 visits are not mandatory; visits every 3 weeks would be preferred, but may be adapted to match local practice.
 10. Cycle 2 to be started 21 days (\pm 2 days) after the start of Cycle 1. Other cycles should be started within +/- 4 days of the 3 weekly treatment cycle intervals.
 11. To be completed before the first dose of lapatinib and capecitabine is administered.
-
13. Second dose of octreotide LAR to be given 28 days (+/- 2 days) after first dose of octreotide LAR.
 14. After 24 weeks treatment with lapatinib and capecitabine. Investigators should continue to treat subjects with lapatinib and capecitabine beyond 24 weeks in accordance with local clinical practice.

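### The SAP's vital-sign summary is poorly placed to show a fall in heart rate on octreotide: required readings in completers come after exposure, and only increases are counted by arm

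*SAP*

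**What the plan says.** **Schedule.** In Protocol Table 16 the row that begins "Weight, Height, Vital Signs (Temp, BP, pulse" is marked at screening and at withdrawal or end of study, and nowhere between. Table 17 and SAP Tables 1-1 and 1-2 agree. The visit lists match: Protocol 7.1.4 (test dose and first LAR dose), 7.1.5 (one week later) and 7.1.6 (three-weekly visits, including the second LAR dose) contain no vital signs; 7.1.8 (completion or early withdrawal) does.

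**Dosing and exposure.** SAP Table 1-1 states "First dose of octreotide LAR to be given 7 days before start of Cycle 1 treatment with lapatinib and capecitabine" and "Second dose of octreotide LAR to be given 28 days (+/- 2 days) after first dose of octreotide LAR". Protocol 1.3.1 says that "the total duration of exposure to clinically relevant concentrations of octreotide is expected to be no more than 12 weeks".

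**Monitoring.** Protocol 4.2 states: "Subjects with hypertension who are randomised to receive octreotide must be monitored to manage the potential risk of bradycardia associated with octreotide use". It gives no measurement times. The Protocol Summary (Study Assessments) leaves vital signs during the study to local practice and the product characteristics of the three drugs.

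**Analysis.** SAP 2.7.9 says: "Summaries of increase in vital signs from the baseline with respect to the categories defined above will be performed". The display gives numbers and percentages with any rise in grade, a rise to grade 2 and a rise to grade 3, at the worst post-baseline value. Blood pressure is divided into Grades 0 to 3; heart rate has three ungraded bands. The same section flags a heart-rate fall to below 60 or rise to above 100 as potentially important, but states no tabulation of the flags by arm.

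**The concern.** Bradycardia is a risk that the protocol itself names for octreotide, and the direction of interest is a fall. The required readings and the planned summary both point elsewhere: most required post-baseline readings are expected after octreotide exposure has ended, and the counts are of increases. A by-arm vital-sign table built this way could look balanced whatever octreotide does to heart rate while it is active. The effect of octreotide on safety and tolerability remains an objective in SAP Table 1-3, so readers of the abbreviated report may take that table as evidence on the question.

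**Working it through.** The plan gives no figure of its own to reproduce. The check is calendar arithmetic, an approximate share of early exits, and a reading of the summary rule.

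**1. Timeline.** Day 0 is the first lapatinib/capecitabine dose.

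- First LAR dose: day −7.
- Second LAR dose: −7 + 28 = day 21 (Week 3), ±2 days.
- End of Week 24: 24 × 7 = day 168.
- Second dose to Week 24: 168 − 21 = 147 days = 21.0 weeks. With ±2 days, 145 to 149 days, or 20.7 to 21.3 weeks.
- Twelve weeks counted from the first LAR dose: −7 + 84 = day 77 (Week 11).
- End of that window to Week 24: 168 − 77 = 91 days = 13.0 weeks.

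Several protocol sections treat octreotide as effective through Week 12 of lapatinib/capecitabine. On that reading the gap is 24 − 12 = 12 weeks, so the result hardly moves.

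**2. Early exits.** Not everyone reaches Week 24. Protocol 3.1 takes the earliest of several events as the end of the study for a subject: "Study completion will be the end of 24 weeks treatment with lapatinib and capecitabine, or disease progression, unacceptable toxicity or subject withdrawal if this is" (the sentence closes by choosing whichever comes first). Protocol 1.1 cites a median PFS for this regimen of 28.6 weeks (95% CI 24.8 to 35.1) in EGF111438; Table 1 gives 27.1 weeks in EGF100151. Assuming exponential progression from the first lapatinib/capecitabine dose, the share progressed by week t with median m is 1 − 2^(−t/m):

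| Median PFS (weeks) | By Week 11 | By Week 24 |
|---|---|---|
| 24.8 | 26.5% | 48.9% |
| 27.1 | 24.5% | 45.9% |
| 28.6 | 23.4% | 44.1% |
| 35.1 | 19.5% | 37.7% |

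So about 20–27% would have an end-of-study visit while exposure may persist, and about 38–49% would leave before Week 24. These shares count progression only; withdrawals for other reasons would raise them.

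**3. What the summary rule does with heart rate.**

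| Baseline band → worst post-baseline band | Increase summary | Flag |
|---|---|---|
| 60–100 → below 60 | Not counted | Flagged, no stated by-arm count |
| Below 60 → 60–100 | Counted, if the bands are taken as ordered | Not flagged |
| 60–100 → above 100 | A rise, but to no defined grade | Flagged, no stated by-arm count |

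The fall of interest is the transition left out of the counts. A recovery from below 60 could be counted as an increase, and the grade 2 and grade 3 columns have no meaning for heart rate.

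**4. Unscheduled readings.** SAP 2.1.3.8 admits unscheduled values to worst-case post-baseline displays, and the vital-sign summary is one. Protocol 9.3.5.2.4 restricts these summaries to scheduled assessments. The two rules give different tables: under the SAP rule, readings taken during exposure can enter; under the protocol rule, they cannot.

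**The case against.** A reader might infer that the vital-sign comparison cannot detect octreotide bradycardia at all. The documents do not support that.

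- The display is worst case post-baseline, not a Week 24 table. It is ECG and LVEF that SAP 2.7.9 reports at Week 24. Under SAP 2.1.3.8, any recorded reading during exposure is eligible.
- Early-exit visits can fall within exposure, as step 2 shows. The 21-week gap describes completers only.
- Protocol 7.1.4 has at least one hour of observation after the test dose, with adverse events recorded. Protocol 7.4.3 makes clinically significant abnormal vital signs adverse events, 7.4.4 requires a specific form for arrhythmias, and SAP 2.7.3 summarises cardiac events as events of special interest. The endpoint for the safety objective is the proportion with adverse events and serious adverse events, not a vital-sign shift.
- Protocol 4.2 covers hypertensive subjects in the octreotide arm only. It is a care instruction, and the product characteristics it may rely on are not available here. It cannot be read as a comparative endpoint for all subjects.

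It is also tempting to say that roughly three quarters of required readings (100% less 20–27%, or 73–80%) fall after exposure. That rests on an assumed exponential, PFS from other trials and progression alone, so it is an approximate upper figure.

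These points remove the absolute claim. They do not fill the gap. Adverse-event enquiry is by open questioning (Protocol 7.4.8), which is unlikely to elicit an asymptomatic fall that nobody has measured. ECG at the final visit is required only if clinically indicated. Unscheduled readings depend on site habit and, because 4.2 applies to one arm, may be more frequent there. Nothing above supplies a by-arm count of heart-rate decreases.

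**Conclusion.** The point holds in a limited form. The vital-sign summary is poorly placed, though not unable, to show a heart-rate decrease on octreotide. For subjects completing 24 weeks, the one required post-baseline pulse falls about 21 weeks after the last LAR dose and 12 to 13 weeks after expected exposure ends. That rests only on the documents' schedule and their stated exposure limit. The share seen earlier, about 20–27% by Week 11, rests on the exponential assumption and the cited PFS. Independently of timing, SAP 2.7.9 counts only increases and uses grades that heart rate does not have, so the relevant direction is flagged but not compared. The consequence is an uninformative table that could be over-read. The primary analysis is not affected.

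**What to change.** In SAP 2.7.9:

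1. Replace the heart-rate grade-increase summary with by-arm counts and percentages of worst-case post-baseline decrease to below 60 and increase to above 100 beats/min. SAP 2.7.8 already does this for ungraded laboratory tests, counting a subject in both directions where both occur.
2. State whether unscheduled readings count, resolving Protocol 9.3.5.2.4 against SAP 2.1.3.8. If they count, show the number of post-baseline readings per subject by arm.
3. Add a note that end-of-study readings in completers fall after expected octreotide exposure and are not evidence on its heart-rate effect.

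The monitoring statement in Protocol 4.2 and the local-practice wording in the Protocol Summary should be reconciled with Table 16. Which monitoring is right is a clinical matter on which this review takes no position.

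The cost is one extra table row and a few lines of SAP text. Enrolment had already stopped for futility when the SAP was written (SAP Introduction), so only the analysis and its wording can still change. The downside is that unscheduled readings may be more frequent in the octreotide arm, which could raise its count of decreases through ascertainment alone; the readings-per-subject line makes that visible but does not remove it.
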